#### 7.1 VISIT SCHEDULE

#### Study Procedures:

- 1) Patients will be screened as described earlier
- 2) Eligible patients will be provided a flyer by ED provider when possible but may also be contacted by telephone once they have been discharged. (Of note: we are being approached by patients who are discharged from the hospital with COVID pneumonia who continue to experience shortness of breath and are requesting a CPAP without having prior knowledge of this study).
- 3) Research will be introduced to the patient, and if they agree to participate, a telephone consent will be conducted (according to IRB requirements including witness). Once patients have enrolled in the study, their PMD will also be notified of their participation. The patient will also be added to the study on EPIC, so that all treating physicians are aware of the patient's participation in our study.
- 4) Once patients have enrolled in the study, a pulse oximeter and a disposable WatchPAT One device will be mailed to the patients (within 24-48 hours of discharge). Orders placed before noon will be delivered the same day by a local durable medical equipment company we are working with. Orders placed past noon, CPAP delivery will be done the subsequent day or upto 48 hours if outside the New York area. Patients who are randomized to the treatment arm will receive a CPAP machine and three full-face masks in addition to the above noted equipment.
- 5) Patient will then be instructed via facetime or other video platform on CPAP setup and use, face mask fitting (those randomized to CPAP), and use of the WatchPAT One and pulse oximeter (for both CPAP and control arm). All participants will wear the WatchPAT one for one night whereas the oximeter will stay on continuously and the patient will report the saturation to us via follow up survey.
- 6) Patients randomized to receive CPAP will be asked to stay in isolation throughout the duration of the study i.e. 72 hours. They will be required to stay in a different room with the door shut and windows open (weather permitting). We will also ask the patient to stop using CPAP during meals or other daily activities. Subjects not on CPAP machine will also be instructed to sleep in a room with windows open (weather permitting).
- 7) Patients will use the CPAP machine as instructed for 72 hours.

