- 8) All patients will be contacted every 6-12 hours to complete follow up assessments. These follow ups will be done via a phone call. If the timing of these follow ups fall between 10pm-6am, the follow up will be deferred until after 6am. After 72 hours, all patients will then be contacted daily until day 14 from randomization. After day 14, research staff will continue to monitor the medical charts for any visits to the hospital. One last contact will be made on day 28.
- 9) After 72 hours, patients will be asked to discontinue using the CPAP and pulse oximeter. If patients wish to continue to use the CPAP, they may do so for up to 7 days from time of randomization.
- 10) The research staff will continue to call all patients daily (after the 72 hour mark) to assess symptoms.
- 11) The patients can also choose to monitor their oxygen saturation beyond the 72 hours of treatment.
- 12) CPAP download is available continuously however we will download data on usage, pressure, leak daily and make adjustments to the mask or CPAP pressure as needed for patient comfort. For patients experiencing significant trouble tolerating high pressure, we will decrease CPAP from 8-10 cm to a fixed CPAP of 5 cm for 2-4 hours after which we will raise it back to 8-10cm for the

- duration of the study. If the patient is not able to tolerate the pressure again, we will reduce it back to 5cm of water pressure for several hours before increasing the pressure. This will be continued until the patient withdraws or 72 hours are completed, whichever occurs first.
- 13) Patients will be asked to track their own oxygen saturation using the provided pulse oximeter and report it when we contact them for the 6-12 hour follow up calls/surveys.
- 14) The sleep apnea test will provide continuous oxygen and breathing data for a period of 12 hours during the 72 hours and will also provide information on oxygen saturation while the patient is asleep.

The outline of the forms that correspond to the study visits can be found in the Appendix, Figure 1. All of these forms are subsequently included in the following appendicies.

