#### SCREENING VISIT

Upon reaching out to patient, the coordinator will confirm enrollment eligibility with the patient prior to consenting.

#### 7.3 VISIT 1

Visit 1 is performed by the coordinator. It consists of the following forms:

- Phone consent
- Enrollment Eligibility Form
- ER Admission Data Form
- Demographics and Subject History Form
- Participant Contact Form
- Medications Form
- CPAP and WatchPAT Assignment Form
- PROMIS questionnaire Form
- Randomization Form
- Respiratory Questionnaire Form
- 1. Once the Mount Sinai team has randomized patient, we will email [contact] with demographics and equipment ordered.
- 2. Community surgical will call patient to confirm address and information, they will then initialize the WatchPAT.
- 3. The pin used will be the DOB in the following format: MMDD
- 4. The pin will be written on the WatchPAT box as well
- 5. Community surgical will then deliver the equipment box to the patient. Patient will receive documents to sign via docusign.

- 6. Once delivery has been made, community surgical will notify PI
- 7. Community surgical will register patient on encoreanywhere once patient has been registered it will take approximately 24 hours before we are able to see the patient on our end

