Proportion of patients with Negative outcome	Control	0.25	0.30	0.35	0.4	0.45	0.5
	СРАР	0.09	0.12	0.16	0.20	0.25	0.29
	Relative reduction in CPAP arm (%)	64	60	54	50	44	42

Randomization Design and Procedure

Patients will be randomized using a 1:1 allocation to CPAP versus control group. The randomization will be stratified by BMI ($\geq=30$ and ≤30), gender and age (≤60 , $\geq=60$). A random permuted block design will be employed, with random blocks of size 2 and 4.

Data Monitoring and Analysis

Primary Efficacy Analysis

The primary efficacy endpoint is the proportion of patients with a negative composite endpoint within 14 days of randomization and will be compared between CPAP and control groups. The null hypothesis is that the proportion of patients with a negative outcome will be the same between patients randomized to CPAP versus control arm. This hypothesis will be tested using a two-sided Fisher's exact test at 0.05 alpha level. The primary analysis will be conducted according to the intention-to-treat principle.

Early stopping rule: If three deaths are observed in the CPAP group, enrollment will be halted pending DSMB review and recommendations. As of April 03, the death rate for COVID-19 positive patients in NYC was 2.99% [95% Clopper Pearson CI= 2.986, 2.997]. The rate is expected to be lower for our patient population. As such, 3 deaths among 100 patients will indicate a proportion of 3% [95% CI: 2.57%, 3.78%].

Analyses of Secondary Endpoints

Safety

Safety analyses will be conducted according to randomization assignment and treatment actually received. Adverse event rates will be calculated as the ratio of the total number of events over 14 days divided by total patient-days at risk for the specific event from randomization. A Poisson model with robust variance estimation will be used to compare SAEs between CPAP and control patients.

Time-to-events outcomes

Time from randomization to event outcomes (Hospitalization or ED visit, ICU admission, intubation and mechanical ventilation) within 14 days of randomization will be compared between randomization groups using a log-rank test or Gray's test in the presence of competing risk of death. In addition, survival at days 14 and 28 post-randomization will be described by Kaplan-Meier curves and a log-rank test will be used to compare survival between the two groups.

Respiratory Function

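### The as-treated safety comparison counts patient-days from randomization although CPAP starts later, so it tends to flatter CPAP for serious events that prevent its start

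*SAP*

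**What the plan says.** The Safety paragraph of the SAP (under Analyses of Secondary Endpoints) plans two comparisons: "Safety analyses will be conducted according to randomization assignment and treatment actually received". One rate formula serves both: "Adverse event rates will be calculated as the ratio of the total number of events over 14 days divided by total patient-days at risk", and the days run "divided by total patient-days at risk for the specific event from randomization". The model is given as: "A Poisson model with robust variance estimation will be used to compare SAEs between CPAP and control patients". The SAP does not say how much CPAP use counts as received, where a CPAP-arm patient who never starts is placed, how days and events before start are assigned, or which of the two comparisons is the main one.

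The protocol puts the start of CPAP after randomization in three steps.

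- **Order.** Section 7.3 (Visit 1): "Once the Mount Sinai team has randomized patient, we will email" the equipment order.
- **Delivery.** Section 7.1, item 4: orders placed before noon arrive the same day. For the others, "Orders placed past noon, CPAP delivery will be done the subsequent day or upto 48 hours if outside the New York area".
- **Set-up.** Section 7.1, item 5, and Section 7.4 (Visit 2): a separate video or telephone call follows delivery.

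Section 10.2 counts an adverse event at any stage of the study, related or not, so events during the wait enter the numerator. Section 7.1, item 12, provides usage data: "CPAP download is available continuously however we will download data on usage, pressure, leak daily".

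**The concern.** A patient can be counted as having received CPAP only after staying well enough, from randomization to set-up, to start it. For any event that prevents start, such as admission, death or withdrawal because of worsening, the waiting days of a CPAP recipient are event-free by construction. The SAP's clock nevertheless puts those days in the recipient's denominator. The patients who did have such an event while waiting are not recipients. If they are placed with the controls, the control rate rises as well; if they are dropped, their events leave the analysis. Either way the as-treated rate ratio tends to fall below its true value. This is immortal-time bias.

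Safety is part of the primary objective in the SAP's General Design Issues, and the trial is open-label. The error runs in the reassuring direction, and the two safety comparisons have equal standing on paper. If they disagreed, the plan gives no rule for which to believe.

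**Working it through.** The SAP gives no figure for the safety analysis, so there is none to reproduce. What follows is an illustration.

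**Inputs from the documents:** 100 patients per arm, a 14-day window, days counted from randomization, delivery the same day to 48 hours later. The 14-day risk of 25% is the lower end of the SAP's range for the control-arm primary outcome (25% to 50%). It is a proxy; no adverse event rate is given.

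**Assumptions:** no true CPAP effect (ratio 1.00), first events only, constant hazard, the same wait for everyone, and every event during the wait prevents start.

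**Formulas.** Hazard λ = −ln(1 − 0.25)/14 = 0.0205 per day. Expected events per arm E = 25, over 25/λ = 1,217 patient-days. Events during a wait of d days: e = 100 × (1 − exp(−λd)). Patient-days hardly differ between groups, so approximately:

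- never-starters moved to control: ratio ≈ (E − e)/(E + e)
- never-starters dropped: ratio ≈ (E − e)/E

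| Wait | e | CPAP events / days | Control events / days, never-starters moved | Ratio, moved | Ratio, dropped |
|---|---|---|---|---|---|
| 6 h | 0.51 | 24.49 / 1,217 | 25.51 / 1,217 | 0.96 | 0.98 |
| 12 h | 1.02 | 23.98 / 1,216 | 26.02 / 1,217 | 0.92 | 0.96 |
| 24 h | 2.03 | 22.97 / 1,216 | 27.03 / 1,218 | 0.85 | 0.92 |
| 48 h | 4.03 | 20.97 / 1,213 | 29.03 / 1,221 | 0.73 | 0.84 |

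The dropped column uses the untouched control rate, 25 / 1,217. At 50% risk the moved ratios are 0.95, 0.91, 0.83 and 0.70.

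**Sensitivity (25% risk, never-starters moved, 24 h and 48 h waits).**

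- Half of early-event patients never start: (25 − 1.02)/(25 + 1.02) = 0.92, and 0.85.
- A quarter never start: 0.96 and 0.92. A tenth: 0.98 and 0.97.
- Hazard three times higher in days 0–3: 0.71 and 0.51.
- Hazard halved in days 0–3: e at 24 h is 1.14, so (25 − 1.14)/(25 + 1.14) = 0.91.
- A true 20% excess after start: the as-treated ratio reads 1.02 and 0.87; by assignment it reads 1.18 and 1.17.

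**Can the direction reverse?** Suppose that 20 of 100 patients in each arm are at half the hazard, overall risk is 25%, and in the CPAP arm these 20 decline the mask and are moved to control. The hazards are then 0.0230 and 0.0115 per day. With a 12 h wait, CPAP has 21.11 events in 957.3 days (0.02205 per day). Control has 25 + 0.91 + 2.97 = 28.89 events (rounded) in 1,475.0 days (0.01959 per day). The ratio is 1.13, against CPAP.

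**Does moving the clock suffice?** With CPAP days counted from start and all waiting days and events counted as not on CPAP, a constant hazard gives 1.00. With the hazard tripled in days 0–3, the ratio at 25% risk is still 0.96, 0.92, 0.84 and 0.70 for the four waits (0.67 to 0.96 across risks of 10%, 25% and 50%), because early high-risk days fall mainly on the untreated side. A landmark at the delivery time gives 1.00 in both cases, as does the analysis by assignment.

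**The case against.** The strongest reply is that the plan already protects the conclusions that matter. The same sentence plans the analysis by assignment. The primary composite is analysed by intention to treat. Hospitalization or ED visit, ICU admission and intubation are compared between randomization groups, and survival between the two groups. An admission during the wait cannot disappear from those analyses. This stands, and it confines the problem to one of two safety comparisons.

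A reader might infer that the SAP moves patients who worsen while waiting into control. It contains no such rule. The bias follows from the usual as-treated conventions, and the plan's silence on which applies is part of the defect.

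A reader might infer that the bias always favours CPAP. It does not: the example with low-risk decliners gives 1.13.

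A reader might infer that the bias could hide aerosol harm to households. The SAP compares family-member conversion by randomized group with Fisher's exact test, without patient-days and without an as-treated split, so that analysis is untouched.

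The size is also open to challenge. Headache, fever or fatigue during the wait need not prevent start, and such events stay in the CPAP group. The 48-hour wait applies only outside the New York area. Section 1.1 of the protocol places decompensation 7 to 10 days after symptom onset, which may put less risk in the wait. These points make the headline ratios an upper bound for adverse events in general. They weigh less for serious events, which are the ones most likely to prevent start and the ones that the Poisson model compares.

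**Conclusion.** The concern holds for the as-treated safety comparison only. A clock that starts at randomization, combined with treatment that starts later, credits CPAP recipients with days in which they could not have had an event that prevents start. If never-starters are moved to control or dropped, this tends to favour CPAP for serious events. Under the stated assumptions the null ratio is about 0.96 to 0.92 for waits of 6 to 12 hours, 0.85 for 24 hours and 0.73 for 48 hours when never-starters move to control; 0.92 (24 hours) and 0.84 (48 hours) when they are dropped; and 0.92 and 0.85 when half of early-event patients never start and are moved. It shrinks toward 1.00 if few early events prevent start and can reverse if low-risk patients decline CPAP.

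The documents give neither the distribution of waits nor adverse event rates, so these are ranges and not predictions. The illustration counts first events, whereas the SAP counts all events. The by-assignment safety analysis, the time-to-event outcomes and household conversion are not affected. The change is worth making because the comparison as specified is biased, not merely under-described, and the correction is cheap.

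**What to change.** In the SAP's Safety paragraph:

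1. Name the comparison by randomization assignment as the main safety analysis and the as-treated comparison as supportive.
2. Define CPAP as received from the first recorded mask-on in the device download. This assumes that the download dates and times use; if it does not, use the time of the Visit 2 set-up call.
3. Treat CPAP as a time-varying exposure: days and events in the CPAP arm before first mask-on count as not on CPAP.
4. Adjust that model for time since randomization. Alternatively, use a landmark at a fixed time after randomization, counting only later events and days in patients still event-free.
5. State that never-starters are not moved to control. Under item 3 their events before start are set against the waiting days of the whole CPAP arm, including those of patients who later start, which a transfer of whole patients would not do.

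The cost is SAP wording and slightly more programming; usage data are already downloaded daily. The as-treated CPAP rate may look less favourable. The as-treated comparison remains non-randomized after these changes, which is why item 1 comes first.

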#### **Secondary endpoints:**

• Time to ICU admission within 14 days of randomization

- Time to intubation and mechanical ventilation within 14 days of randomization
- Time to death within 14 and 28 days of randomization
  - Degree of improvement in oxygen saturation within 14 days of randomization
  - Improvement in respiratory symptoms of cough, shortness of breath, etc via respiratory symptom questionnaire within 14 days of randomization
  - Adverse events and conversion rates of COVID family members in CPAP vs control within 14 days of randomization
  - Percent of patients electing to continue CPAP for greater than 72 hours
  - Time to hospital admission or ED visit within 14 days of randomization

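### Adverse-event rates are planned only over 14 days, although CPAP is used for 3 to at most 7 days, and no treatment-period comparison stands beside them

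*SAP*

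**What the plan says.** The Safety paragraph of the SAP (under Analyses of Secondary Endpoints) fixes the numerator and denominator: "Adverse event rates will be calculated as the ratio of the total number of events over 14 days divided by total patient-days at risk". The clock starts at assignment, since the denominator is "patient-days at risk for the specific event from randomization". The grouping is given as "Safety analyses will be conducted according to randomization assignment and treatment actually received". The only model named is for serious events: "A Poisson model with robust variance estimation will be used to compare SAEs between CPAP and control patients".

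On exposure, Protocol section 7.1, item 7 says "Patients will use the CPAP machine as instructed for 72 hours". Item 9 adds an option: "If patients wish to continue to use the CPAP, they may do so for up to 7 days from time of randomization". Item 4 allows equipment delivery on the same day, the next day, or up to 48 hours later outside the New York area. Section 7.3 shows that the equipment is ordered after randomization.

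Neither document defines a 72-hour, 7-day or on-treatment window for adverse events.

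**The concern.** The SAP's General Design Issues put safety beside efficacy in the primary objective. For efficacy the plan does use a treatment-period window: two of the four components of the primary composite are confined to the first 72 hours. The adverse-event rate has no such window. It pools the days on CPAP with at least 7, and as planned 11, later days on which both arms are off the device.

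Analysing by the treatment patients in fact had does not change this. As written, it moves patients between groups and does not restrict which days are counted.

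At stake is how a null result is read. A harm confined to the time on the mask would be averaged with days on which little difference may exist. A ratio near 1 over 14 days could then be reported as showing that CPAP is safe while in use, which that analysis alone cannot show.

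**Working it through.** The documents state no expected adverse-event rate, effect size or power for safety, so there is no safety figure to reproduce. The SAP's power table concerns the primary endpoint. It does reproduce (exact two-sided Fisher power 80.9% to 85.4% with 100 per arm) but does not bear on this point.

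**Inputs from the documents.** Window of 14 days from randomization (SAP, Safety). CPAP use *d* of 3 days as planned and 7 at most (Protocol 7.1, items 7 and 9). 100 patients per arm, 1:1 (SAP). The share continuing past 72 hours is unknown in advance; it is itself a secondary endpoint ("Percent of patients electing to continue CPAP for greater than 72 hours").

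**Assumptions.** Constant background of 0.02 or 0.05 events per patient-day, that is 0.28 or 0.70 events per control patient over 14 days. The rate is doubled only while CPAP is in use, with no excess afterwards. Follow-up is complete and counts are Poisson. The test is two-sided at 5%, which the SAP states for the primary test only.

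**Step 1: time off the device.** (14 − 3)/14 = 79% with planned use; (14 − 7)/14 = 50% with maximum use.

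**Step 2: rate ratio seen in a window of *W* days.** Ratio = [*d* × 2 + (*W* − *d*)]/*W*.
- 14 days, 3 of use: 17/14 = 1.21.
- 14 days, 7 of use: 21/14 = 1.50.
- 14 days, with 25%, 50% or 75% of patients continuing to day 7 (mean use 4, 5 or 6 days): 1.29, 1.36 or 1.43.
- 7 days, 3 of use: 10/7 = 1.43.
- 7 days, 7 of use: 14/7 = 2.00.

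**Step 3: power.** Wald test of the log rate ratio, by simulation of Poisson counts. Hand check for 0.05 per day and 3 days of use in the 7-day window: expected events are 100 × 0.05 × 7 = 35 (control) and 100 × 0.05 × 10 = 50 (CPAP). Then ln(50/35) = 0.357, standard error √(1/35 + 1/50) = 0.220, z = 1.62, and power is about 37%, against 36% simulated.

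| Background per patient-day | Days of use | 14-day window | Day-7 window |
|---|---|---|---|
| 0.02 | 3 | 11% | 17% |
| 0.05 | 3 | 22% | 36% |
| 0.02 | 7 | 38% | 57% |
| 0.05 | 7 | 75% | 93% |

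**Step 4: why not 72 hours from randomization.** Suppose 72 hours of use begin at delivery. Power for a doubled rate in a 3-day window is then:

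| Background per patient-day | No delay | 1-day delay | 2-day delay | 14-day rate, any delay |
|---|---|---|---|---|
| 0.02 | 26% | 14% | 6% | 11% |
| 0.05 | 60% | 34% | 13% | 22% |

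With a two-day delay the 3-day window holds one day of CPAP and does worse than the 14-day rate. The day-7 window still holds all three days (2 + 3 = 5, within 7), so its power is unchanged.

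**Step 5: sensitivity to the assumptions.** For a doubled rate, the 14-day ratio is in general 1 + the share of 14-day background events that fall on CPAP days. A 10% share gives 1.10. A background that halves every 3 to 7 days gives 1.52 to 1.34 with 3 days of use. For rare events, take 0.05 per control patient over 14 days and 3 days of use. Expected counts are 5.0 vs 6.1 over 14 days and 2.5 vs 3.6 to day 7. The normal approximation, which flatters counts this small, gives about 6% and 7%. No window rescues that comparison.

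**The case against.** The strongest reply is that the 14-day rate by randomized arm is a proper estimate of the 14-day effect of being assigned CPAP. A reader might infer that it is biased towards finding no harm. The documents do not support that. Protocol section 1.1 expects decompensation 7 to 10 days after symptom onset, and Aim 1 follows patients partly for late effects of CPAP, so the later days are where delayed harm would appear. This stands, and it is why the 14-day analysis should stay.

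A reader might also infer that most of the power to see harm is lost. That is not general. With 7 days of use the relative loss against a day-7 window is at most about a third, and the days of use are unknown in advance. For rare serious events, which are what the Poisson model is named for, sample size is the limit. Events that occur only because of CPAP, with no background, are not diluted in the between-arm ratio.

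The size of the background is itself uncertain. The table under Clinical Endpoints in Protocol section 10.2 requires no reporting of common COVID symptoms such as fever or fatigue, while section 10.6 asks for all events to be recorded.

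Finally, other harm analyses exist. They include desaturation within 72 hours in the primary composite, household conversion, time to hospitalization, ICU admission and intubation, a halt at three CPAP deaths, and prompt reports to the DMC chair. These limit the consequence, but none compares adverse-event rates over the treatment period.

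**Conclusion.** The gap is real but limited. The SAP has one adverse-event rate, over 14 days from randomization, for a device used for 3 to at most 7 of those days. Under a constant background and an excess confined to use, a doubled rate appears as about 1.2 to 1.5. A day-7 window shows the same harm as 1.4 to 2.0 and had more power in all four scenarios in the Step 3 table.

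The size rests on assumed background rates and on the assumption of no excess after CPAP stops; the documents supply neither. The conclusion that no treatment-period comparison is planned rests on the text alone. The planned analysis is incomplete, not invalid.

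**What to change.** In the SAP's Safety paragraph, keep the 14-day analysis. Beside it, prespecify the same rate calculation and the same Poisson comparison with robust variance, by randomized arm, for randomization to day 7, with an identical window in both arms. This covers all CPAP use that the protocol permits, including late delivery, and keeps the randomized comparison. Do not make randomization to 72 hours the main window, because delivery delay can leave little CPAP time in it. State that a null 14-day ratio will not by itself be taken as evidence of safety during use.

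The cost is a few lines of SAP text and one more run of the model. Event timing is already needed for the planned patient-days at risk, and patients are contacted every 6 to 12 hours to 72 hours and daily to day 14 (Protocol 7.1, item 8). The downsides are one more analysis to report, fewer events in the shorter window, and continued reliance on the 14-day rate for delayed harm.
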